#### **4.5.2 Secondary Efficacy Endpoints**

Type I error for secondary endpoints is controlled through a hierarchical testing framework. The  $\alpha$  level is 0.05. Following the two statistical comparisons described in Section 4.5.1 for the primary endpoint (Arm A versus Arm  $C_{\text{control}}$  and Arm B versus Arm  $C_{\text{control}}$ ) the secondary endpoints are included in the hierarchy in the following order:

- A versus C randomized comparison: all bleeds
- B versus C randomized comparison: all bleeds
- A versus C randomized comparison: treated joint bleeds
- B versus C randomized comparison: treated joint bleeds
- A versus C randomized comparison: treated spontaneous bleeds
- B versus C randomized comparison: treated spontaneous bleeds
- D intra-patient: all bleeds
- D intra-patient: treated bleeds

- A versus C randomized comparison: Haem-A-QoL physical health at 24 weeks
- B versus C randomized comparison: Haem-A-QoL physical health at 24 weeks

#### **4.5.2.1 All Bleeds**

The definition of all bleeds is described in Section 2.3.2.1. The analysis methodology is the NB regression model or the Van Elteren test, as described for the primary endpoint in Section 4.5.1.

#### **4.5.2.2 Treated Spontaneous Bleeds**

The definition of treated spontaneous bleeds is described in Section 2.3.2.2. The analysis methodology is the NB regression model or the Van Elteren test, the same as for the primary endpoint.

#### **4.5.2.3 Treated Joint Bleeds**

The definition of treated joint bleeds is described in Section 2.3.2.3. The analysis methodology is the NB regression model or the Van Elteren test, the same as for the primary endpoint.

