### **2.3.2.4 Treated Target Joint Bleeds**

Target joints are joints into which repeated bleeds occur (i.e.,  $\geq 3$  bleeds into the same joint over the last 24 weeks prior to study entry). The target joints prior to study entry are identified through the eCRF. The bleeds in target joints during the efficacy period are defined by first selecting the bleeds that fulfill the definition of a treated joint bleed and then counting how many of these occurred in a target joint as defined prior to study entry. The locations to be taken into account are shoulder, elbow, wrist, fingers/thumb, hip, knee, ankle, sole/heel, and toes. Left and right sides of the same joint type are considered to be separate joints.

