### **4.4 ANALYSIS OF TREATMENT GROUP COMPARABILITY**

Comparisons between the treatment arms of demographic data (e.g. age, sex, race/ethnicity, weight, and height) and baseline disease characteristics (e.g., number of bleeds in the past 24 weeks, previous hemophilia treatments, and number of target joints) will be conducted to establish if any observed differences between the treatment arms are not due to imbalances in patient characteristics at baseline. Only descriptive analyses are planned, and no formal statistical tests will be applied.

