#### **4.5.1 Primary Efficacy Endpoint**

The primary efficacy objective is to evaluate the clinical effect of prophylactic emicizumab compared with no prophylaxis on the number of bleeds over time. The definition of a bleed is described in Section [2.3.1](#). The primary endpoint is based on treated bleeds.

The comparison of the number of bleeds over time between the randomized treatment arms will be performed using an NB regression model, which accounts for different follow-up times, with the patient’s number of bleeds as a function of randomization and the time that each patient stays in the study (the length of the efficacy period) included as an offset in the model. The model also includes the number of bleeds ( $<9$  or  $\geq 9$  according to the eCRF data) in the last 24 weeks prior to study entry as a stratification factor. This analytic model estimates the rate ratio,  $\lambda_t/\lambda_c$ , which quantifies the risk of bleeding associated with prophylactic emicizumab ( $\lambda_t$ ) in comparison to no prophylaxis ( $\lambda_c$ ). Statistical significance is controlled at the 2-sided, 0.05 alpha ( $\alpha$ ) level.

Of note, hierarchical testing is used to account for multiple testing and the first test to be included in the hierarchy is the emicizumab 1.5 mg/kg/wk maintenance dose versus

control. The second test will be 3 mg/kg/2wks maintenance dose versus control. A global approach using a model statement (within GENMOD) with a 3-level categorical effect for treatment (“1.5 mg/kg/wk,” “3 mg/kg/2wks,” or “no prophylaxis”) and an appropriate contrast statement will allow both tests to be performed via the following hypothesis

$H_0$  (null hypothesis): Rate Ratio = 1 versus  $H_1$  (alternative hypothesis): Rate Ratio  $\neq$  1.

Statistical significance at the prespecified  $\alpha$  level will be based on a Wald testing procedure. Bleed rates for prophylactic emicizumab and no prophylaxis and the rate ratio will be presented and include 95% CIs.

The number of bleeds can also be annualized for each patient using the following formula:

$$ABR = (\text{Number of bleeds} / \text{Total number of days during the efficacy period}) \times 365.25.$$

Both the model-based method (estimated ABR from the NB model) and the method using the above formula (calculated ABR) will be used to describe the study results.

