#### **4.5.5 Subgroup Analyses**

Comparative subgroup analyses describing the primary endpoint, treated bleed rate, will be conducted for the randomized portion of the study. In addition, estimated ABR including 95% CI will be calculated for all treatment arms in each subgroup. Note, due to the small sample size, all subgroup analyses will be highly sensitive to variability caused by individual patients and need to be interpreted with caution. No p-values will be calculated.

The pre-specified subgroups are:

- Age: < 18, ≥ 18
- Age: < 65, ≥ 65
- Race: Asian, Black or African American, White, Other
- Number of bleeds during 24 weeks prior to study entry: ≤ 9, > 9

- Number of target joints: no target joint, any target joint

Subgroup analyses are subject to having sufficient patients in a subgroup to provide meaningful results.

In addition, region- and/or country-specific analyses will be performed to support regulatory submissions as needed.

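### The two alpha-controlled joint-bleed tests leave out baseline target-joint status: a missed, probably modest gain in efficiency, not an error

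*SAP*

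**What the plan says.** The hierarchy in SAP 4.5.2 lists "A versus C randomized comparison: treated joint bleeds" and then "B versus C randomized comparison: treated joint bleeds". They follow the two primary tests and the two all-bleeds tests, so they are fifth and sixth. Six tests come after them: spontaneous bleeds (A, B), the Arm D intra-patient comparisons (all bleeds, treated bleeds) and Haem-A-QoL physical health (A, B).

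For the method, SAP 4.5.2.3 says "The analysis methodology is the NB regression model or the Van Elteren test, the same as for the primary endpoint". The primary model in SAP 4.5.1 is a negative binomial (NB) regression with a three-level treatment effect, a follow-up offset and one baseline term, the number of bleeds (<9 or ≥9) "in the last 24 weeks prior to study entry as a stratification factor". Protocol 6.5.2 likewise applies the primary NB model to joint bleeds.

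Target-joint status is available and is used elsewhere:
- SAP 2.3.2.4: "The target joints prior to study entry are identified through the eCRF". A target joint has at least 3 bleeds in the 24 weeks before entry. The Protocol Appendix 1 footnote on medical history has it recorded at screening in all arms.
- SAP 4.4 describes arms at baseline by "number of bleeds in the past 24 weeks, previous hemophilia treatments, and number of target joints".
- SAP 4.5.5 has the subgroup "Number of target joints: no target joint, any target joint", for the treated bleed rate only.
- SAP 4.5.2.6 analyses target-joint bleeds as an endpoint outside the hierarchy.

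**The concern.** The stratum counts bleeds at any site. A patient with 12 muscle bleeds and one with 12 bleeds into the same knee share a stratum, although one would expect different joint-bleed rates. Target-joint status is close to a baseline version of the outcome. Between-patient variation that it could explain stays in the NB dispersion and widens the interval for the joint-bleed rate ratio. With 17 controls the arms may also differ by chance in the share of patients with a target joint, and the estimate then moves with that difference.

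The SAP already accepts endpoint-specific adjustment: the Haem-A-QoL test in SAP 4.5.2.5 includes its own baseline score. At stake is the chance of passing two tests on which six others depend.

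**Working it through.** **Inputs from the plan** (SAP 2.4 and 4.5.1): ABR 4 versus 14; variance 10 × mean; 0.5 time units of follow-up; 30 versus 15 patients for the power statement and 34 versus 17 planned; 2-sided alpha 0.05.

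**Reproducing the plan's power.** For the log rate ratio,

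SE² = (1/(λt·t) + kt)/nt + (1/(λc·t) + kc)/nc.

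On the annual scale, variance = 10 × mean gives k = 9/mean: 9/4 for emicizumab and 9/14 for control.

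- 30 versus 15: SE² = (0.5 + 2.25)/30 + (0.143 + 0.643)/15 = 0.0917 + 0.0524 = 0.1440, so SE = 0.380. With log(14/4) = 1.253, power is 91.0%. The stated figure of more than 90% is reproduced.
- 34 versus 17: SE = 0.357, power 94.0%.

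That base is not robust. Simulating 30/30/15 with one common dispersion and the stratum term gives 87.5%.

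**Inputs the documents do not give, so assumed:** joint share of bleeds s = 0.5–0.9, target-joint prevalence p = 0.5–0.85, joint-bleed rate with versus without a target joint r = 1.5–3, and the same 4/14 ratio for joint bleeds.

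**Closed form, 34 versus 17.** The variation that the covariate explains is CV² = p(1−p)(r−1)²/(1+p(r−1))². Removing it leaves k′ = (1+k)/(1+CV²) − 1.

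Middle case, s = 0.75, p = 0.7, r = 2:
- CV² = 0.21/2.89 = 0.073; k′ = 2.03 (emicizumab) and 0.53 (control).
- SE falls from 0.367 to 0.349, which is 5% in SE and about 10% in variance.
- Power rises from 92.7% to 94.8%.

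Over the whole assumed range, SE falls by 1–16% and power rises by 0.5–6.5 points. This form does not allow for the stratum term already in the model.

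**Simulation with the stratum term fitted.** 3,000 trials per setting of 34/34/17; target-joint prevalence 10 points above or below p according to stratum; a 1.5-fold stratum effect except in the first row, which has none.

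| s, p, r | A vs C power, without → with | Both tests, without → with | Empirical SD of log rate ratio |
|---|---|---|---|
| 1, 0.7, 1 (no effect) | 91.5 → 92.1% | 86.0 → 86.9% | 0.360 → 0.367 |
| 0.75, 0.7, 1.5 | 92.1 → 92.9% | 86.9 → 88.3% | 0.369 → 0.370 |
| 0.75, 0.7, 2 | 92.7 → 94.9% | 88.0 → 91.4% | 0.363 → 0.353 |
| 0.75, 0.5, 2 | 93.5 → 95.4% | 87.7 → 91.7% | 0.361 → 0.350 |
| 0.75, 0.7, 3 | 92.7 → 95.5% | 88.4 → 92.9% | 0.365 → 0.342 |
| 0.5, 0.7, 2 | 90.1 → 92.1% | 84.2 → 87.1% | 0.387 → 0.379 |

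With a real effect the gain is 0.8–2.8 points per test and 1.4–4.5 points for passing both. The no-effect row shows 0.6 points with no fall in SD, so gains below about one point should not be counted. In the middle case the chance of stopping at these two tests falls from 12.0% to 8.6%. Rejection under the null is 5.6–6.8% without the term and 5.3–7.2% with it. The small excess over 5% is common to both models.

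**Weaker effect or more dispersion.** Assume control joint ABR 9, p = 0.6, r = 3, residual dispersion 0.64 and a modest stratum effect. The gain is then 5–8 points at a rate ratio of 0.4, and 0–3 points from a base of 94–96% at 4/14. Raising the dispersion to 1.5 at 4/14 gives about 5 points.

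**Chance imbalance.** The SD of the difference in prevalence is √(p(1−p)(1/34 + 1/17)). At p = 0.7 this is 0.136, and with r = 2 it shifts the log rate ratio by 0.136 × 1/1.7 = 0.080, about 0.2 SE. Over the assumed range the shift is 0.04–0.15, against an SE of 0.36–0.39.

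**The case against.** The strongest reply is that nothing is broken. The model includes the only randomization factor, randomization makes the test valid, and using one model for all bleed endpoints is a legitimate choice that Protocol 6.5.2 itself makes. Changing SAP 4.5.2.3 alone would make two confirmatory tests depart from the protocol. All of that stands.

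A reader might infer that chance imbalance with 17 controls biases the joint-bleed tests or inflates alpha. It does not: the standard error already allows for it, and the null rejection rates are alike with and without the term. A reader might also infer that the plan ignores bleeding history or target joints. It adjusts for prior total bleeds, and target joints appear in the baseline tables, a subgroup and a separate endpoint.

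Target-joint status and the stratum cover the same 24 weeks and are probably correlated, so part of the signal is already captured. Entry requires at least 5 bleeds, so prevalence could be high, which leaves little to gain. The covariate comes from medical records, whose bleed recording Protocol 3.3 calls inconsistent. Protocol 4.5.8 speaks of major joints, whereas SAP 2.3.2.4 also lists fingers/thumb, sole/heel and toes. These points lower the expected gain.

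The Van Elteren objection (17 controls over four cells) is met by leaving that test alone. Adjustment then depends on NB convergence, which is tolerable if stated in advance.

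**Conclusion.** The point holds as a missed efficiency gain. Two alpha-controlled tests omit a likely predictor that the trial already collects. Adding it leaves the target of estimation unchanged, because the rate ratio under a log link is collapsible, and it leaves type I error as it was.

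The size rests on assumed prevalence, assumed effect and assumed correlation with the stratum. It is about 0–3 points of power per test at 4/14 with near-planning dispersion, about 5 points there if residual dispersion is 1.5 with a 3-fold effect, 5–8 points at a rate ratio of 0.4 with a 3-fold effect, and close to zero if nearly everyone falls in one category. Gains of up to 11 points can be produced, but only with a rate ratio of 0.4 and target-joint status independent of the stratum. The documents support neither: SAP 2.4 plans 4 versus 14, and the two variables overlap by definition.

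**What to change.** Before arm-level data are examined, amend SAP 4.5.2.3 to state that:
- the NB model for treated joint bleeds, A versus C and B versus C, also includes baseline target joint (none/any), coded as for the subgroup in SAP 4.5.5 and citing the definition used;
- this is an addition to the model in Protocol 6.5.2;
- the model without the term is reported as a sensitivity analysis, and is used if the adjusted fit does not converge;
- the Van Elteren fallback stays stratified by <9 or ≥9 only.

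The cost is one parameter, a few sentences and a small departure from one common model for all bleed endpoints. No new data are needed. If arm-level data have already been seen, the adjusted model should be supportive only.

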#### **4.5.2.4 Intra-Patient Comparison—Previous Prophylactic Patients**

[figure not shown]
The definition of treated bleeds and all bleeds for the intra-patient comparison (Section 4.1) is the same as described for the primary and secondary endpoints. The analysis methodology will be applied for Arm D (previous prophylactic patients) using the same NB regression model as for the primary endpoint with the exception that the SAS GENMOD procedure will include a REPEATED statement, to account for the intra-patient comparison. For intra-patient analysis of Arms A and B, see Section 4.5.2.6.

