4.5.2 Medical History and Demographic Data

Medical history includes clinically significant diseases, procedures, use of alcohol and drugs of abuse within the past year, and medication allergies. In particular, sites should record whether the patient has any history of FVIII inhibitor, anaphylaxis or known thrombophilia. It should also include all medication taken in the 4 weeks prior to screening (including prescription, over-the-counter, and herbal/homeopathic remedies and therapies) or in the 24 weeks prior to screening for medications intended to treat osteopenia or osteoporosis. If imaging tests of bone health (e.g., densitometry, dual energy X-ray absorptiometry [DEXA]) were performed in the year prior to screening, the results should be recorded. Finally, number of bleeds during the 24 weeks prior to study enrollment should be documented, as well as the number of school/work days missed and number of days hospitalized during the 24 weeks prior to study entry.

Demographic data will include age, sex, and self-reported race and ethnicity.

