## **2. STUDY DESIGN**

Study BH30071 is a randomized, multicenter, open-label, Phase III clinical study will enroll patients aged 12 years or older with severe hemophilia A (intrinsic FVIII level < 1%)

without inhibitors against FVIII. Approximately 85 patients who received episodic treatment with FVIII prior to study entry and experience at least 5 bleeds over the prior 24 weeks (annual bleed rate [ABR]  $\geq 10$ ) will be randomized in a 2:2:1 ratio to the following regimens:

- Emicizumab prophylaxis at 3 mg/kg/week (wk) subcutaneously for 4 weeks, followed by 1.5 mg/kg/wk subcutaneously (Arm A)
- Emicizumab prophylaxis at 3 mg/kg/wk subcutaneously for 4 weeks, followed by 3 mg/kg/every 2 weeks (2wks) subcutaneously (Arm B), or
- No prophylaxis control arm (Arm C)

Randomization will be stratified according to the number of bleeds patients experienced over the last 24 weeks prior to study entry,  $<9$  versus  $\geq 9$  (or ABR 18), to ensure a balance of patients with lower versus higher number of bleeds in all arms. All patients will continue usual episodic treatment with FVIII in case of a breakthrough bleeding event.

[figure not shown]
In addition, 40–60 patients with severe hemophilia A who received FVIII prophylaxis prior to study entry will be enrolled and receive emicizumab prophylaxis at 3 mg/kg/wk subcutaneously for 4 weeks, followed by 1.5 mg/kg/wk subcutaneously (Arm D). To improve the validity of historical comparison in this group, at least 40 patients will be observed on FVIII prophylaxis in NIS BH29768 for a period of at least 24 weeks before enrolling in Arm D of this study.

The study schema is shown [Figure 1](#).

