### **2.3.2.5 Intra-Patient Comparison**

In the intra-patient comparison (on All Bleeds and on Treated Bleeds as defined in Section 2.3.2.1 and Section 2.3.2.2, respectively), only patients who participated in NIS BH29768 are included. This is because it is possible to apply the detailed bleed definitions only if the data are collected with the same granularity for both time periods. Of note, for some episodic patients who participated in NIS BH29768, the total time in that study prior to enrollment in Study BH30071 may be less than 24 weeks.

The efficacy period in NIS BH29768 is defined as the time from the first entry on the electronic, handheld device or site data entry system to the day the patient completed the study, which may occur between 1 day and a few days prior to

enrollment/randomization in Study BH30071. Usually, the date of the first BMQ entry in NIS BH29768 is the date the Training Module on the electronic, handheld device is completed. The end of the efficacy period in NIS BH29768 is defined as the date of withdrawal or date of study completion or on the day of the clinical cutoff, whichever occurs earlier.

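### Read literally, SAP 4.5.2.4 keeps the <9/≥9 prior-bleed factor in the Arm D intra-patient model, where it overlaps the comparator outcome and pushes the emicizumab/NIS rate ratio upward

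*SAP*

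**What the plan says.** SAP 4.5.2.4 fits the Arm D comparison "using the same NB regression model as for the primary endpoint with the exception that the SAS GENMOD procedure will include a REPEATED statement". The primary model in SAP 4.5.1 has a three-level treatment effect, an offset for the length of the efficacy period, and the number of bleeds (<9 or ≥9, from the eCRF) "in the last 24 weeks prior to study entry as a stratification factor". Protocol 4.5.2 gives the source of that count: "number of bleeds during the 24 weeks prior to study enrollment should be documented".

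In the intra-patient comparison "only patients who participated in NIS BH29768 are included" (SAP 2.3.2.5). The comparator period is the "time from the first entry on the electronic, handheld device or site data entry system to the day the patient completed the study", and the SAP expects it to end between one day and a few days before enrolment. SAP 2 adds that "at least 40 patients will be observed on FVIII prophylaxis in NIS BH29768 for a period of at least 24 weeks before" they enter Arm D.

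SAP 3.1 places Arm D outside the randomisation. Protocol 4.1.1 sets no bleed-count requirement for these patients. The comparison enters the hierarchy of SAP 4.5.2 as "D intra-patient: all bleeds", followed by treated bleeds and then by the two Haem-A-QoL tests.

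**The concern.** In the randomised comparison the <9/≥9 factor is a baseline covariate, measured before either of the compared outcomes. In Arm D one of the two compared outcomes is the pre-enrolment bleed count, and the factor is a cut of nearly that same count over nearly that same window. Patients placed in the ≥9 stratum were selected for a high comparator count, so part of their later fall is regression to the mean. Patients in the <9 stratum show the opposite drift. Negative binomial (NB) weighting gives the ≥9 stratum less weight than its share of bleeds, so the drift in the <9 stratum dominates and the ratio rises.

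Both Arm D tests are alpha-controlled. If emicizumab is better than FVIII prophylaxis, the effect is understated and power is lost, and a missed Arm D test also stops the hierarchy before the Haem-A-QoL tests. The factor has no design basis here, because nothing was stratified in Arm D.

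**Working it through.** **The plan's own figure first.** The documents give no power or rate ratio for the Arm D comparison, so the check on the NB set-up is the primary power in SAP 2.4: above 90% with 30 vs 15 patients, ABR 4 vs 14, variance 10 × mean, 0.5 years. The dispersion is k = (variance − mean)/mean². That is (40 − 4)/16 = 2.25 on emicizumab and (140 − 14)/196 = 0.643 in control.

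Var(log RR) = [1/(0.5×4) + 2.25]/30 + [1/(0.5×14) + 0.643]/15 = 0.0917 + 0.0524 = 0.1440, so SE = 0.380.

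Power = Φ(ln(14/4)/0.380 − 1.96) = 91.0%. This agrees with the SAP.

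**Inputs for Arm D.** SAP 2.4 gives 40 to 60 patients, with ABR 4 and variance 4×10 on emicizumab. Assumptions that the documents do not supply: the same rate and dispersion in the NIS period, the true ratio, the within-patient correlation, and the agreement between eCRF and questionnaire counts.

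**How many patients reach nine bleeds.** The mean 24-week count is 4 × 168/365.25 = 1.84. With k = 2.25, P(≥9) is about 4.4%: 1.8 of 40 patients or 2.6 of 60. In about 17% (n = 40), 11% (n = 48) and 7% (n = 60) of simulated trials nobody reaches nine, and the factor drops out.

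**Mechanism by hand** (identical frailty in both periods, true ratio 1, 24 weeks each). Given a NIS count y, the expected later count is 1.84 × (0.444 + y)/(0.444 + 1.84) = 0.805 × (0.444 + y), where 0.444 = 1/k.

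- ≥9 stratum: mean NIS count 12.48, expected later count 10.41, ratio 0.83.
- <9 stratum: mean NIS count 1.35, expected later count 1.45, ratio 1.07.

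The NB estimating equations are Σ x(y − μ)/(1 + kμ) = 0. With k = 0 (Poisson weights) the common ratio solves to exactly 1.00. With k = 2.25 it solves to 1.056. A smaller k, as when the stratum absorbs some dispersion, changes little (1.054 at k = 1.46). The upward shift therefore comes from the factor and the NB weights together.

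**Large-sample simulation** (60,000 patients, paired NB counts with gamma frailty, NB model with patient-clustered robust SE, 24-week NIS period):

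| True ratio | Without factor | With factor, identical frailty | With factor, correlation 0.8 | With factor, correlation 0.5 |
|---|---|---|---|---|
| 0.30 | 0.30 | 0.314 | 0.327 | 0.347 |
| 0.50 | 0.50 | 0.527 | 0.553 | 0.587 |
| 1.00 | 1.00 | 1.057 | 1.113 | 1.174 |
| 1.50 | 1.50 | 1.586 | 1.670 | 1.774 |
| Shift | none | about 5% | 10–12% | 17–18% |
| SE ratio (with/without) | | 1.08–1.09 | 1.02–1.03 | 0.97–0.99 |

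**Trial-sized simulation** (600 trials per case, true ratio 0.5; independence and exchangeable working correlations gave the same results). Power is counted over trials in which at least one patient reached nine bleeds. At n = 48 it is 96.8% without the factor and 90.6% with it (identical frailty), and 72.5% against 53.8% (correlation 0.5). The mean SE goes from 0.175 to 0.193 with identical frailty, where the per-trial ratio averages about 1.12, and from 0.285 to 0.282 at correlation 0.5.

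**Less overlap.** With identical frailty, a 36-week NIS period gives a shift of 3–4%, 48 weeks 2–3%, an eCRF that misses 20% of bleeds about 3%, and the last two together 1–2%. At correlation 0.5, the 20% under-recording still leaves about 12%.

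**The case against.** The best reply is that SAP 4.5.2.4 lists no covariates. Its reference to the same model cannot be fully literal, because a three-level arm effect does not exist in a single arm. Protocol 6.5.1 describes the factor as belonging to the randomisation, and Protocol 6.5.2 asks only for a similar model, so a programmer might well drop it. This stands to the extent that retention is the literal reading and not an explicit covariate list. It does not make the text safe: it shows that an alpha-controlled model needs an adaptation that nobody has written down.

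Second, the overlap is not exact. The factor comes from the eCRF, while the outcome comes from the NIS questionnaire under the detailed bleed rules, and NIS follow-up may exceed 24 weeks. This is right, and it is why the lower figures above are part of the result.

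Third, few patients reach nine bleeds and the shift runs against emicizumab, so it does not favour a superiority claim. That also stands. It limits the seriousness but leaves the power loss.

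A reader might infer two stronger things. One is that the bias is always toward no effect. It is upward, so it is toward no effect only when the true ratio is below 1. A true 1.00 is estimated above 1, and a true 1.50 moves further from 1. The other is that the confidence interval always widens. The SE ratio runs from about 0.97 to 1.12, and at correlation 0.5, where the bias is largest, there is no widening.

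**Conclusion.** The point holds as a specification fault with a known direction. On the literal text, the Arm D model conditions on a cut of nearly its own comparator count, and the estimated ratio is too high. A true ratio of 0.50 would be estimated at about 0.53 to 0.59 with a 24-week NIS period. Where frailty is identical across periods, a longer NIS period or eCRF under-recording brings the shift down to 1–3%. The loss of power is modest if patients' bleeding tendency is stable and substantial if it is not.

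These sizes rest on the assumed NIS rate and dispersion, true ratio, within-patient correlation and capture of bleeds in the eCRF, none of which the documents give. The direction was the same in every case with a shared window. The documents do not support a claim that the plan favours emicizumab here, or that the factor is explicitly listed for Arm D.

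**What to change.** In SAP 4.5.2.4, replace the reference to the primary model with the model itself: NB regression with a period effect (emicizumab vs NIS), the log of each period's length as offset, and patient as the repeated subject, without the <9/≥9 factor. Make the same statement for the pooled Arms A and B analysis in SAP 4.5.2.6. The factor was a true randomisation stratum for those patients, but that analysis is also within-patient and lies outside the hierarchy.

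The cost is a sentence or two. No data collection, sample size or test order changes. In the simulations the model without the factor recovers the true ratio. Its SE is smaller or, at correlation 0.5, larger by about 1% (0.285 vs 0.282).
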